**Statistical Methods:**

All data collected will be presented in data listings. Data from subjects excluded from an analysis set will be presented in the data listings, but not included in the calculation of summary statistics. For categorical variables, frequencies, and percentages will be presented. Continuous variables will be summarized using descriptive statistics (number of subjects, mean, median, standard deviation, minimum, and maximum). Data will be tabulated by treatment, across active treatment groups when applicable, with all placebo subjects pooled into a single group.

All evaluable data from subjects in the analysis sets will be included in the analyses. No adjustment or imputation will be utilized for missing values or for subjects who withdraw prior to completing the study.

Baseline values will be defined as the last assessment prior to investigational product administration and per period if applicable.

Definition of Reversal of Anticoagulation – Clotting Time by WBCT

- Complete reversal is defined as a return of mean WBCT to  $\leq 110\%$  of baseline up to and including 1 hour following test article administration.
- Complete and sustained reversal of anti-coagulation is defined as a return of mean WBCT to  $\leq 115\%$  of baseline at all time points between 1 and 5 hours following test article administration. Dose escalation or de-escalation will be determined by this criterion.

Details of all statistical analyses will be specified in a separate statistical analysis plan (SAP) that will be finalized prior to data base lock.

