The pharmacodynamics results show that at pre-study drug on Day 3, mean observed WBCT after edoxaban dosing increased to similar levels in the placebo group and ciraparantag treatments. Over the one to six hours postdose interval (inclusive) after the first ciraparantag dose, complete reversal for WBCT was achieved in a higher percentage of subjects in the active treatments (82.9% for all doses) compared to the placebo group (60.0%). Across the 30 mg ciraparantag to 360 mg PER977 treatments, the rate of complete reversal at 30 mg was slightly lower (62.5%) while the rate was similar for 60 mg or higher dose levels (88.9% to 100%). Both evaluable subjects (100%) in the 15 mg PER977 treatment had partial reversal. None of the subjects in any of the placebo or active treatments had percent-of-baseline WBCT >190% at any time point (i.e., no reversal).

Results of statistical comparisons showed ciraparantag had no impact on re-anticoagulation with edoxaban as measured by WBCT at pre-study drug on Day 4 versus pre-study drug on Day 3. Over the 1 to 6 hour postdose interval (inclusive) after the second ciraparantag dose on Day 4, the rates of complete reversal were comparable to Day 3. Overall, 88.6% of the subjects in the active ciraparantag treatments and 53.3% of subjects in the placebo group had complete reversal. Across the 30 mg to 360 mg active treatments, the rate of complete reversal was slightly lower (66.7%) for 180 mg while the rate was similar for all other dose levels (87.5% to 100%). None of the subjects in any of the placebo or active treatments had percent-of-baseline WBCT >190% at any time point (i.e., no reversal).

Treatment comparisons of percent-of-baseline WBCT showed lower values compared to placebo following 60 mg to 360 mg ciraparantag on Day 3 that were statistically significant at most time points between five minutes to three hours after the end of injection (geometric least-squares [LS] ratios ranged from 86.52% to 93.70%); and following 30 mg to 360 mg ciraparantag on Day 4 at most time points between five minutes to six hours after the end of injection (geometric LS ratios ranged from 84.91% to 95.71%). On both study days, WBCT at different dose levels in the active ciraparantag treatments returned to baseline within the 0.083-hour to 0.75-hour time points. Post-baseline WBCT in placebo-treated subjects did not decrease to baseline level until the 1-hour (Day 4) to 1.5-hour (Day 3) post-study drug time point.

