**6.9.2 Pharmacodynamic Assessment**

Blood samples (2 ml) for measuring of clotting time by WBCT will be collected at the following time points:

Day 1: pre-apixaban baseline (within 1 hr. prior to dosing)

Day 4: post-apixaban at 2.75 hr and post-study drug at 15, 30, 45 minutes, and 1, 3, 5, 24 hrs. (only subjects with at least 20% increase of clotting time from the Day 1 pre-apixaban baseline will be randomized).

TriPLICATE WBCT will be done Day 1 pre-apixaban baseline, post-apixaban at 2.75 hrs. and post-study drug at 1 hr on Day 4.

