### Statistically Significant Complete Reversal

- Statistically significant complete reversal, relative to mean placebo WBCT, is defined as  $p<0.05$ , (one tailed) from the comparison of means between treatment and placebo at 15, 30, 45 minutes or 1 hour post study drug administration as measured by one-way Analysis of Variance at study completion. Distribution diagnostics will be performed to assure assumptions associated with using ANOVA are met. Analysis of Means (ANOM) methods will be used to compare means and variances across groups. These methods will be appropriate to test if any of the group means are statistically different from the overall mean or if the group standard deviations are statistically different from the root mean square error (RMSE). Tukey HSD multiple comparison procedure will be used to test for all pairwise differences among the means (Tukey 1953, Kramer 1956). This test is an exact alpha-level test if the sample sizes are the same, and conservative if the sample sizes are different (Hayter 1984).

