- k. Apixaban oral tablet will be administered as 10 mg BID (Q12) after meal on Days 1-3. On Day 4, a single dose 10 mg apixaban will be administered after breakfast on the morning and the study drug injection will follow approximately 3 hours later. Stroke assessment will be performed at approximately 3 hours post-apixaban dosing on the morning (\pm 1-hour window) on Day 1 to 4.
- l. Blood samples for WBCT will be collected on Day 1 pre-apixaban (as baseline), Day 4 post-apixaban at 2.75 hrs. and post-study drug at 15, 30, 45, minutes, and at 1, 3, 5, and 24 hrs. Only subjects with at least 20% increase of clotting time from Day 1 pre-apixaban baseline will be randomized for study drug treatment.
- m. Blood samples for PK assessment of apixaban and ciraparantag and its metabolite will be collected on Day 4 post-apixaban at 2.75 hr and post-study drug at 15, 30, 45 minutes, and at 1, 3, 5, and 24 hrs. For apixaban PK, a pre-apixaban blood sample on Day 1 will also be collected.
- n. Follow-up will be performed by telephone on Day 7-10. Subjects may be discharged from the study after the telephone call if all AEs have resolved to the satisfaction of the Investigator.

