4.6.3 Dose Proportionality

The dose proportionality of exposure PK parameters for PER977 and BAP ($AUC_{(0-\infty)}$, $AUC_{(0-\text{last})}$, and C_{max}), over the administered dose range will be investigated using the following power model:

$$\log (\text{PK parameter}) = a + b \times \log (\text{Dose})$$

Dose proportionality will be assessed statistically using the above power model approach with the logarithm of PK parameters as the dependent variables and the logarithm of the dose as the independent variable for subjects who receive one dose at a given dose

interval. The intercept (a) and the slope (b) together with their 90% confidence interval (CI) will be estimated and summarized for each PK parameter. Parameters ‘a’ and ‘b’ will be estimated using an ordinary least-squares approach or the equivalent. Dose proportionality will be declared if the 90% CI for the slope parameter ‘b’ lies entirely within the critical region (0.80, 1.25).

In addition, the dose proportionality of exposure PK parameters for PER977 and BAP ($AUC_{(0-\text{inf})}$, $AUC_{(0-\text{last})}$, and C_{\max}) will be evaluated between adjacent means using an ANCOVA model. The ANCOVA model for the log-transformed PK parameters (separate model for PER977 and BAP) will include dose (categorical) and gender as fixed effects, and weight as a covariate. A summary of the results of the ANCOVA, and pairwise comparisons by analyte including the dose ratio (%), exposure ratio (%), and 90% confidence interval will be presented.

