4.7 Efficacy Analyses

4.7.1 Primary Analysis

The efficacy endpoint will be the PD assessment of clotting time by WBCT; the efficacy endpoint will be summarized at observed time points and as change from baseline (and/or ratio) values using descriptive statistics and graphical presentations.

Change-from-baseline and percent-of-baseline will be calculated for all efficacy endpoints. Baseline for all efficacy endpoints will be defined as the pre-apixaban sample (pre-apixaban on the morning of Day 1).

The anticoagulant effect of apixaban will be evaluated by comparing WBCT measured at pre-PER977 (three hours post-apixaban on the morning of Day 4) versus baseline (pre-apixaban on the morning of Day 1). For the purposes of the efficacy analyses, subjects with percent-of-baseline WBCT at pre-ciraparantag $<120\%$ (i.e., $<20\%$ increase) will be considered as apixaban non-responders and will be excluded from all efficacy summaries and assessments.

Listings of individual efficacy variable collection times as well as derived sampling time deviations (where applicable), will be provided.

Individual observed and change from baseline values at scheduled time points and efficacy parameters will be listed and summarized by treatment. In addition, the nature of reversal of anticoagulation based on the definition of reversal of anticoagulation below using WBCT will be summarized and then listed for each subject.

Definition of Reversal of Anticoagulation

- Complete reversal is achieved for a treatment group if the mean WBCT is $\leq 110\%$

of baseline at any post-baseline time point up to and including 1 hour following test article administration. Complete reversal is achieved for a subject if WBCT is $\leq 110\%$ of baseline at any post-baseline time point up to and including 1 hour following test article administration.

- Complete and sustained reversal of anti-coagulation is achieved for a treatment group if the mean WBCT is $\leq 115\%$ of baseline at all time points between 1 and 5 hours (inclusive) following test article administration. Complete and sustained reversal of anti-coagulation is achieved for a subject if WBCT is $\leq 115\%$ of baseline at all time points between 1 and 5 hours (inclusive) following test article administration.

Statistically Significant Complete Reversal

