- Statistically significant complete reversal, relative to mean placebo WBCT, is defined as $p < 0.05$, (one tailed) from the comparison of means between treatment and placebo at 15, 30, 45 minutes or 1 hour post study drug administration as measured by one-way Analysis of Variance (ANOVA) at study completion. Distribution diagnostics will be performed to assure assumptions associated with using ANOVA are met. The one-tailed Dunnett's test will be used for comparisons of treatment means.

Analysis of Means (ANOM) methods will also be used to compare means and variances across groups. These methods will be appropriate to test if any of the group means are statistically different from the overall mean or if the group standard deviations are statistically different from the root mean square error (RMSE).

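### The WBCT test against placebo names neither a covariate nor a response scale, so precision available from the pre-dose WBCT may be lost

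*SAP*

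**What the plan says.** SAP 4.7.1 defines statistically significant complete reversal by a one-sided 5% comparison of each dose with placebo, "as measured by one-way Analysis of Variance (ANOVA) at study completion", using a one-tailed Dunnett test. Protocol 9.8 has the same model, "as measured by one-way Analysis of Variance at study completion", with Tukey HSD; SAP 4.11 records the switch to Dunnett. Neither text names a covariate. Neither says whether the means compared are of observed WBCT, change from baseline or percent of baseline.

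Two pre-dose WBCT values are available. Protocol 6.9.2 schedules triplicates: "WBCT will be done Day 1 pre-apixaban baseline, post-apixaban at 2.75 hrs. and post-study drug at 1 hr on Day 4". Both values are needed for entry (SAP Table 1, footnote l): "Only subjects with at least 20% increase of clotting time from Day 1 pre-apixaban baseline will be randomized for study drug treatment".

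The plan uses them elsewhere. In SAP 4.7.1, Day 1 is the efficacy baseline, and "Change-from-baseline and percent-of-baseline will be calculated for all efficacy endpoints". The same section uses the Day 4 value to describe the apixaban effect and to exclude non-responders. SAP 4.7.2 uses the triplicates for inter-observer variability. (SAP 3.5 and protocol 9.7 describe baseline differently; I follow the efficacy-specific Day 1 definition in SAP 4.7.1.)

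Covariate adjustment is already planned for PK: the log-scale model in SAP 4.6.3 "will include dose (categorical) and gender as fixed effects, and weight as a covariate".

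**The concern.** A clotting time depends partly on the subject's own level and on how strongly that subject responded to apixaban. The two pre-dose readings measure both, and the second is taken shortly before study drug. If they predict post-dose WBCT, a one-way ANOVA leaves that variation in the error term of every dose-placebo comparison.

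Expressing the outcome as percent of Day 1 removes the subject's level. It also carries Day 1 measurement noise into the outcome and leaves the Day 4 level unused. An ANOVA on observed WBCT would not remove even the subject's level, and the SAP wording does not exclude that choice.

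This test is the plan's inferential statement on the primary objective. It rests on 12 subjects per arm with no power calculation behind it.

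**Working it through.** **Inputs from the documents.** Three cohorts of 16 give 3 × 16 = 48, which reproduces the planned number. Randomisation at 3:1 gives 12 per dose, and placebo pooled over cohorts gives 3 × 4 = 12. Error df are 48 − 4 = 44 for the ANOVA and 42 with two covariates. The test is one-sided at 0.05 with Dunnett's correction for three doses; the critical value is about 2.12 at either df. There is no planned power, SD or correlation to reproduce, so every variance below is an assumption.

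**Generic check, one covariate with correlation ρ to the outcome, same slope in all arms.** With unadjusted variance set to 1, ANCOVA leaves 1 − ρ² and a change score (or log ratio to baseline, equal SDs) leaves 2(1 − ρ). Power is from the noncentral t with noncentrality δ / (σ√(1/12 + 1/12)).

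| ρ | ANCOVA variance | Change-score variance | Difference detectable at 80% power, ANCOVA |
|---|---|---|---|
| 0.3 | 0.91 | 1.40 | 1.17 SD |
| 0.5 | 0.75 | 1.00 | 1.06 SD |
| 0.7 | 0.51 | 0.60 | 0.88 SD |

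The unadjusted ANOVA detects 1.21 SD. Using Day 1 only as a subtrahend or divisor raises the error when ρ is below 0.5. ANCOVA leaves (1 + ρ)/2 of the change-score variance: 0.65, 0.75 and 0.85.

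**Simulation of this design (log scale, 10,000 trials per case).** Day 1 = L + noise and Day 4 = L + A + noise, as triplicate means, where L is the subject's level and A the apixaban effect. Subjects are kept only if Day 4/Day 1 ≥ 1.20, and the post-dose value is a single reading. Assumed log-SDs: L 0.10 or 0.20; A 0.05 or 0.10; single reading 0.05 or 0.10; occasion 0.03. The mean post-apixaban level is 140% of Day 1, or 125% in some cases. The slope on A is 1 in placebo and 0, 0.5 or 1 in active arms. The true active/placebo ratio is 0.90, inside the range in the earlier edoxaban trial (protocol 1.2.4: "geometric least-squares [LS] ratios ranged from 86.52% to 93.70"%). The comparison is one dose against placebo at one time point, ANOVA on log percent-of-baseline versus ANCOVA on log Day 1 and log Day 4.

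| Slope on A in active arms | Cases | Power gain (points) |
|---|---|---|
| 0 (drug removes the between-subject apixaban effect) | 12 | 1.7 to 4.8 (e.g. 81.3% to 86.1%) |
| 0.5 | 8 | 5.2 to 18.2 |
| 1 (removes none of it) | 12 | 4.3 to 34.9 |

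At slope 0 the standard error is 3% to 11% smaller.

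- **If the ANOVA were run on log observed WBCT:** slope-0 power is 17.0% to 53.2%, and the gain from ANCOVA is 14 to 73 points.
- **If the covariates predict nothing:** 44.4% falls to 42.7%, 63.1% to 61.0% and 79.1% to 77.0% (true differences of 0.8, 1.0 and 1.2 SD).
- **If one covariate is linked to outcome in placebo only (ρ 0.7 and 0):** no gain, 44% against 44%.
- **Type I error:** familywise 4.7% to 5.1% for ANOVA on percent-of-baseline and 4.8% to 5.1% for ANCOVA.
- **Scale:** with log Day 1 in the model, the contrasts and standard errors are identical for log observed and log percent-of-baseline WBCT.

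**At the level the test is named for.** A ratio of 0.90 from 140% leaves active arms at 0.90 × 140% = 126% of Day 1, above the 110% that defines complete reversal. With active arms set at 110% instead (L 0.10, 24 cases, 1,500 trials each):

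| Mean post-apixaban level | ANOVA power | Gain (points) |
|---|---|---|
| 140% | 98.2% to 100% | 0 to 1.6 |
| 125% | 74.8% to 100% | 0 to 9.3 (at most 2.1 at slope 0) |

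If success at any of the four time points counts, ANOVA power at 110% is at least 98.5% in all 24 cases and the gain is at most 1.4 points.

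**The case against.** The strongest reply is that little may be lost. If the drug works as hoped and the response is percent-of-baseline, the ANOVA already has ample power. The largest gains need either active arms that keep all the between-subject apixaban variation or a response scale that does not match the reversal definition. The 0.90 ratio comes from another anticoagulant. This stands, and it is why the point is graded as a cheap improvement. It does not remove the gain for a dose with partial effect, which the study intends to include. At a ratio of 0.90, counting any of the four time points, gains are about 0 to 7 points at slope 0 and up to about 22 at slope 1.

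A reader might infer that neither pre-dose value is used to reduce error. For Day 1 that is not established: SAP 4.7.1 calculates percent-of-baseline from it and defines reversal on that scale, and the test wording leaves the scale open. Only the absence of the Day 4 value is certain.

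A reader might also infer that dose decisions are affected. The protocol synopsis ties them to the 115% sustained-reversal definition instead: "Dose escalation or de-escalation will be determined by this criterion".

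A last objection is that a new model should not displace the planned distribution checks. That is right, and the fix keeps them.

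**Conclusion.** The point holds as a possible loss of precision. The test has no covariate and no named response scale, Day 4 pre-dose WBCT plays no part in it, and Day 1 enters at most as a divisor or subtrahend. The documents do not support calling the test biased, invalid or underpowered: randomisation protects it, its simulated error rate is nominal, and no power is claimed.

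The size depends wholly on assumed variances:

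- about 2 to 5 points of power at one time point for a ratio of 0.90 when the drug removes the between-subject apixaban effect, and up to about 35 when it does not;
- about 0 to 9 points, near zero in most cases, when active arms reach 110% of baseline;
- a loss of about 2 points if the covariates predict nothing.

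The unnamed scale is the larger exposure, because observed WBCT would cost far more than the missing covariates do on percent-of-baseline.

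**What to change.** In SAP 4.7.1, before database lock:

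- Name the response as log WBCT as a percent of Day 1 baseline.
- At 15, 30, 45 minutes and 1 hour, replace the one-way ANOVA with ANCOVA: treatment (three doses, pooled placebo) plus log Day 1 and log Day 4 2.75-h WBCT, each the mean of its triplicate.
- Keep the one-tailed Dunnett contrasts, now on adjusted means, and keep the distribution diagnostics.
- Report the unadjusted ANOVA on the same scale as a sensitivity analysis.
- Log the change in SAP 4.11.

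The cost is SAP text, a small programming change and 2 of 44 error degrees of freedom. No new data are needed, and no correctly randomised subject drops out, because the 20% rule requires both covariates. After lock, the adjusted model could only be supportive.

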As of August 15, 2016, ciraparantag has been evaluated in four clinical studies of single escalating doses of ciraparantag following administration edoxaban (PER977-01-001; NCT01826266), unfractionated heparin (PER977-01-002; NCT02206087), and enoxaparin (PER977-01-003; NCT02206100), and following anticoagulation and re-anticoagulation with edoxaban (PER977-02-001; NCT02207257, see protocol section 1.2). These studies have shown that, a single intravenous (IV) dose of ciraparantag demonstrated reversal of anticoagulant drug (e.g. edoxaban and enoxaparin) induced anticoagulation for different testing periods following study drug administration.

This phase 2 study is intended to extend the findings of efficacy, safety and pharmacokinetics (PK) characteristics of the study drug, ciraparantag; a randomized, single-blind, placebo-controlled assessment of the efficacy and safety of ciraparantag administered to healthy volunteers measuring clotting times using WBCT is an acceptable study design. Further data on efficacy, safety, tolerability, and PK characteristics will be collected.

A total of three dosing cohorts (Cohorts 1-3) are planned. The planned doses of ciraparantag or placebo (administered as a volume equivalent of ciraparantag) have been evaluated as single and repeat IV doses from 5 mg ciraparantag acetate (3 mg ciraparantag) up to 600 mg ciraparantag acetate (360 mg ciraparantag) in previous protocols (PER977-01-001, PER977-01-002, PER977-01-003, and PER977-02-001).

The goal of the study is to explore the dose range of ciraparantag that reverses the anticoagulation induced by therapeutic doses of apixaban at steady state. The study is intended to establish a dose of ciraparantag that fully reverses steady-state apixaban, to evaluate at least one dose above the reversal dose to establish a therapeutic index, and at least one partial or no effect dose.

This statistical analysis plan (SAP) covers the detailed procedures for performing statistical analyses and for producing tables, listings, and figures (TLFs) in the study.

2 Study Objectives

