2.2 Secondary Objectives

The secondary objectives of this study are:

- To evaluate the safety and tolerability of ciraparantag 60 mg (100 mg ciraparantag acetate), 120 mg (200 mg ciraparantag acetate), and 30 mg (50 mg ciraparantag acetate), and additional cohorts if necessary administered approximately 3 hours after 10 mg apixaban administration at steady state.

- To assess the PK characteristics of apixaban and of ciraparantag and its primary metabolite, 1,4-bis(3-aminopropyl) piperazine (BAP).

[figure not shown]
3 Study Design and Methods

This is a randomized, single-blind, placebo-controlled assessment of the efficacy and safety of ciraparantag administered to healthy volunteers measuring clotting times using WBCT. All subjects will undergo screening up to 36 days prior to enrollment.

Randomization will take place on Day 4 after administration of apixaban. Subjects will be enrolled sequentially into one of up to three cohorts. If the Screening visit takes place within 3 weeks prior to check-in, the check-in procedures may be modified to exclude redundant procedures at the discretion of the Investigator. There will be a safety review after completion of treatment in one cohort and before initiation of treatment in the subsequent cohort.

Subjects (n=16 per cohort) will be randomized in a 3:1 ratio to receive ciraparantag or placebo (saline for injection). [Figure 1](#) depicts the experimental design.

Figure 1 Dose Schema

All subjects will receive 10 mg apixaban for 3.5 days (twice daily Q12 on Days 1-3 and once on the morning of Day 4). On Day 4, approximately 3 hours after administering apixaban, study drug or placebo will be intravenously administered. Study drug will be administered only to those subjects who have a minimum increase in clotting time of 20% (as measured by WBCT) above Day 1 pre-apixaban baseline levels at the pre-study drug time point on Day 4 (i.e., 2.75 hours post-apixaban). Any subject who does not have a minimum increase in clotting time of 20% above Day 1 pre-apixaban baseline levels at the pre-study drug time point on Day 4 will be discontinued from the study and replaced. At approximately 3 hours following apixaban a single IV dose of study drug (ciraparantag or placebo) will be administered.

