3.5 Data Handling

Summaries for continuous variables will include the descriptive statistics for number of subjects (n), mean (arithmetic and/or geometric), standard deviation (SD), minimum (min), median, and maximum (max). Summaries for categorical (discrete) variables will include the number of subjects and/or percentage of subjects in a particular category.

Conventions for presentation of numerical data:

Min and max values will be presented to the same number of decimal places as the Electronic case report form (eCRF) data. Means and medians will be presented to one more decimal place than the eCRF data. Standard deviations will be presented to two more decimal places than the eCRF data.

Plasma and serum concentration data will be displayed in listings.

In general, individual and summary values will be displayed as follows:

- (1) Values > 0.0001 and < 1 will be reported to 4 decimal places (e.g., 0.0123).
- (2) Values > 1 and < 10 will be reported to 3 decimal places (e.g., 1.023).
- (3) Values > 10 and < 100 will be reported to 2 decimal places (e.g., 10.23).
- (4) Values > 100 and < 1000 will be reported to 1 decimal place (e.g., 100.2).
- (5) Values > 1000 or equal to 0 will be reported as a whole integer (e.g., 1000).

Values for T_{\max} , t_{last} and $t_{1/2}$ will be reported to 2 decimal places.

All evaluable data from subjects in the analysis sets will be included in the analyses. No adjustment or imputation will be utilized for missing values or for subjects who withdraw prior to completing the study, neither will analyses be restricted to subjects with complete data. All tabulations will include all placebo subjects pooled across cohorts.

Baseline values will be defined as the last assessment prior to investigational product administration and per period if applicable.

Change from Baseline is defined as [Post-baseline Value – Baseline Value].

4 Data Analysis

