4.11 Changes from Pre-Specified Analyses

In the statistical analysis of complete reversal, Tukey HSD multiple comparison procedure was replaced by one-tailed Dunnett's test for comparison of treatment and placebo means.

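### The SAP's one-tailed Dunnett test has no step-down; a step-down version has the same familywise 5% at a given time point, never rejects less, and can gain up to about 17 points of power at the lowest dose, depending on the dose-response shape

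*SAP*

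**What the plan says.** SAP 4.7.1 sets the significance criterion for complete reversal at a one-tailed 0.05, from a one-way ANOVA of WBCT against placebo at 15, 30 or 45 minutes or 1 hour. For the group comparisons, the one-tailed Dunnett's "test will be used for comparisons of treatment means". SAP 4.11 records the change from the protocol: "Tukey HSD multiple comparison procedure was replaced by one-tailed Dunnett's test for comparison of treatment and placebo means". Neither section mentions a step-down or any other stepwise procedure.

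The design comes from elsewhere in the SAP:
- Section 1: "A total of three dosing cohorts (Cohorts 1-3) are planned". The doses are 30, 60 and 120 mg (SAP 2.2).
- Section 3: "Subjects (n=16 per cohort) will be randomized in a 3:1 ratio to receive ciraparantag or placebo".
- Section 3.5: "All tabulations will include all placebo subjects pooled across cohorts".
- Section 1 also says that the study should include "at least one partial or no effect dose".

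SAP 3.4 states that there was no formal sample size calculation. No SD, effect size or power is given. SAP 4.7 plans no simultaneous confidence intervals for efficacy; the only intervals in the SAP are the 90% intervals for dose proportionality in 4.6.3.

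**The concern.** A single-step Dunnett test holds each dose to the penalty for three comparisons, even after the other doses have been shown to differ from placebo. The step-down form relaxes the penalty as doses are rejected. The usual reason to stay with the single-step form is that it gives simple simultaneous confidence bounds, and the SAP does not plan any.

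The contrast that can benefit most is the lowest dose. With 12 subjects per group, it is likely to be the hardest to separate from placebo. Failing to detect a real effect there could lead the report to describe a weakly active dose as having none.

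**Working it through.** **Inputs.** Sixteen per cohort at 3:1 gives 12 active and 4 placebo. Three cohorts give 12 per dose and 3 × 4 = 12 pooled placebo, taking the pooled placebo as the ANOVA control. Hence 48 subjects in 4 groups, error df = 48 − 4 = 44, and a correlation between dose-placebo contrasts of 12/(12 + 12) = 0.5. One-sided level 0.05. The documents give no power figure to reproduce. Effect sizes below are assumptions, in units of the common SD, in the direction of lower WBCT than placebo.

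**Critical values.** For k doses still under test, c(k) solves P(max of k contrasts ≤ c) = 0.95 for the equicorrelated multivariate t (correlation 0.5, 44 df), by numerical integration:

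| Doses still under test | c(k) |
|---|---|
| 3 | 2.120 |
| 2 | 1.965 |
| 1 | 1.680 |

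Single-step uses 2.120 for every dose. Step-down compares the largest statistic with 2.120, the next with 1.965 and the last with 1.680, stopping at the first failure. Since 1.680 < 1.965 < 2.120, it cannot lose a single-step rejection, and none was lost in any simulated setting.

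**Familywise error at one time point.**

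| Truth | Single-step | Step-down |
|---|---|---|
| No dose works | 5.0% | 5.0% |
| One very effective dose | 3.6% | 5.0% |
| Two very effective doses | 2.0% | 5.0% |

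**Low-dose power when both higher doses are certain to be rejected.** The t statistic has noncentrality d × √(12/2) = d × 2.449. Power is P(t > 2.120) for single-step and P(t > 1.680) for step-down.

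| Low-dose effect d (SD) | Single-step | Step-down | Gain (points) |
|---|---|---|---|
| 0.5 | 19.5% | 33.1% | 13.6 |
| 0.75 | 39.5% | 56.6% | 17.0 |
| 1.0 | 63.1% | 77.8% | 14.8 |
| 1.2 | 79.2% | 89.4% | 10.2 |
| 1.5 | | | 3.9 |
| 2.0 | | | 0.2 |

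These are simulated powers, with gains taken before rounding. The exact maximum gain is 16.9 points, at 0.78 SD. The gain reaches 14 points only for d between 0.52 and 1.04.

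**Other dose-response shapes.**

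| Shape | Dose where gain is counted | Gain (points) |
|---|---|---|
| Equal effects at all doses, 0.6 to 1.5 SD | each | 3.0 to 7.6 |
| Effects in ratio 1 : 1.5 : 2, low dose 0.5 / 0.75 / 1.0 SD | lowest | 8.5 / 14.5 / 14.2 |
| Both higher doses at 1.25 SD, low dose 0.5 / 0.75 / 1.0 SD | lowest | 12.6 / 14.6 / 11.5 |
| Lowest dose inert, top dose certain, middle 0.6 to 1.2 SD | middle | 4.1 to 6.0 |
| Lowest dose inert, middle and top equal, 0.8 to 1.2 SD | middle | 2.7 to 3.1 |
| Only the top dose works | top | about 0.1 or less |

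**Any of four time points.** The results above are for one time point. The SAP's criterion can be met at any of four, with no stated adjustment. With two doses at 2 SD and the lowest dose inert, the chance of falsely declaring the lowest dose effective at one or more time points is as follows (correlation between time points assumed):

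| Correlation | Single-step | Step-down |
|---|---|---|
| 0.9 | 3.8% | 8.8% |
| 0.7 | 5.5% | 12.3% |
| 0.5 | 6.4% | 14.5% |

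If no dose works, the chance of at least one false dose claim under this rule is the same for both versions: about 9% at correlation 0.9 and 17% at 0.3.

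**The case against.** Dunnett is a standard and valid many-to-one test, and the SAP had already improved on the all-pairs Tukey procedure. This is a small Phase 2 volunteer study without a power target. Reversal is classified by thresholds of 110% and 115% of baseline, and the protocol synopsis ties dose escalation or de-escalation to the 115% rule, so no stated dose decision turns on the low-dose p-value. A test against placebo also does not separate partial from complete reversal. All of this stands. It limits the importance of the point but gives no reason to prefer the less powerful of two tests with the same error guarantee.

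A reader might infer that the plan gives away 14 to 17 points of power at the lowest effective dose. The documents do not support that as a property of the plan. It is close to the ceiling, and it needs both higher doses virtually certain to be rejected together with a low-dose effect of about 0.5 to 1.0 SD. No SD or effect size is given to establish that case, and the SAP expressly allows for a no-effect dose. Earlier edoxaban results do not settle it. Protocol 1.2.1 describes initial signs of reversal at 30 mg and full reversal at 60 mg and above, which fits the favourable shape. It also reports significant differences at 30 mg with only four treated subjects, which suggests an effect so large that little would be gained. Apixaban is in any case a different anticoagulant.

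A reader might also infer that changing the test alone is free of risk. It is not. Under the unadjusted any-of-four rule, the slack in the single-step test partly offsets the multiplicity over time, and removing that slack more than doubles the false-positive rate for an inert low dose.

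**Conclusion.** The point holds as an inexpensive improvement, not as an error. At any one time point, step-down Dunnett has the same one-sided 5% familywise error and rejects at least as much; that needs no assumed effect size. The gain ranges from about 0 to about 17 points according to the dose-response shape, and the documents do not say which shape to expect. The figures assume 12 evaluable subjects in each of four groups, pooled placebo as control, normal data with a common SD, and the single-step reading of the SAP. The error guarantee does not extend to the present rule of success at any of four time points, so the recommendation depends on that rule being dealt with as well.

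**What to change.** In SAP 4.7.1, replace the one-tailed Dunnett's test by a *one-tailed step-down Dunnett test (familywise 5%)*, with a matching entry in 4.11. In the same change, either name one confirmatory time point or summary measure for the test, or state an adjustment across the four time points. Do not adopt the step-down test under the current unadjusted rule. Make the change before database lock, the limit that Protocol 9.1 sets for finalizing the SAP.

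The cost is one sentence for the test and a decision on the time points, with no extra subjects or visits. There are two downsides. Step-down Dunnett gives adjusted p-values but no simple matching simultaneous confidence bounds, although none are planned for efficacy. It also leaves no slack if group variances differ, so the comparison of variances already planned in 4.7.1 should be kept.
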